This protocol amendment include a fourth arm, which will be a 10 mg Leuprolide Oral Tablet administered BID for 28 days (Treatment “D”). As with the previous arms of the study, PD markers will be evaluated weekly during the 28 days of dosing and for a 28 day wash out period. The tablet formulation will revert to the more successful formulation used in the Phase 1 study, where the bioavailability was 3.0%. The amount of leuprolide projected to be absorbed into the circulation is 0.6 mg per day (3% of 20 mg). This is roughly equivalent to the 0.5 mg per day delivered by daily subcutaneous injection that was effective in treating uterine fibroids, and is approximately 60% of the 1 mg approved SC dose administered in the Phase 1 study. There is a further safety margin for the Treatment “D” dose of 10 mg bid: the Lupron Depot® 3.75 mg label contains the statement, “In early clinical trials using daily subcutaneous leuprolide acetate in patients with prostate cancer, doses as high as 20 mg/day for up to two years caused no adverse effects differing from those observed with the 1 mg/day dose.” Given the low bioavailability of the oral dose, about 3%, a substantial safety margin is assured.

The comparative PK/PD evaluations will form important bridges between different routes of leuprolide administration using both the company’s proprietary data and relevant published findings.

Additional information on Leuprolide Oral Tablet can be found in the Investigator's Brochure.

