### **Treatment Period (28-Day Dosing Cycle)**

#### **Treatment Day – 1 (Check-in) – Treatments “A”, “B” and “C”**

This visit will take place within 40 days of the Screening Visit.

Subjects will report to the investigational clinic at least 11 hours before next-day dosing and will remain domiciled until the completion of all study procedures on Treatment Day 2.

- Collect information on changes in medical history/current medical conditions and concomitant medication since the Screening Visit, to confirm that excluded medications have not been taken or have appropriately been discontinued and washed out.
- Collect information on the date of onset of the LMP if it took place after the Screening Visit.
- Assess body weight and vital signs (temperature, pulse rate, respiratory rate, systolic and diastolic blood pressure).
- Collect samples for urine drug screen and urine cotinine tests.

- Perform serum pregnancy test ( $\beta$ -hCG) for all subjects; subjects with positive results are not eligible for the study.
- Perform alcohol breath test.
- Review inclusion and exclusion criteria to confirm eligibility.
- The subjects will undergo a supervised overnight fast of at least 10 hours in duration. A light snack will be served on the evening of admission to the clinical facility. No liquid or food intake is allowed during the fast, except water, which is permitted up until 1 hour prior to study drug administration.

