**Treatment Day 1 – Treatment “D”**

This visit will take place within 40 days of the Screening Visit. Subjects enrolled to the third oral dose (Treatment “D”) will have a dosing initiation visit scheduled 5-9 days before the anticipated start of their next menstrual cycle, based on their self-reported menstrual cycle length and the day the current menstrual cycle began.

- Verify no change in subject’s health status before dosing.
- Perform urine pregnancy test; subjects with positive results cannot be enrolled in the study.
- Collect samples for urine drug screen and urine cotinine tests.
- Perform alcohol breath test.
- Assign randomization number.
- Obtain baseline PK blood sample immediately (within 10 minutes) prior to dosing.
- The fasting period will be -2h to +2h for the first administered dose.
- Obtain baseline PD blood sample (LH, FSH, E2, and progesterone) immediately (within 30 minutes) prior to dosing.
- Administer study drug in the morning. Oral tablets will be administered with 240 mL of water. Perform mouth check following oral tablet dosing to ensure compliance.
- Assess body weight and vital signs (temperature, pulse rate, respiratory rate, systolic and diastolic blood pressure) predose (within 2 hours prior to dosing). Note: The vital signs will be assessed prior to the first oral dosing
- Record adverse events (AEs) and concomitant medication use.
- Release subject from the clinical site 2 hours after dosing.

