**Treatment Day 27 (Check-in): Treatment “A” and Treatment “B” groups only**

Subjects from Treatment groups “A” and “B” will report to the investigational clinic at least 11 hours before next-day morning oral dosing and will remain domiciled until the completion of all study procedures on Postdosing Day 1.

- Verify no change in subject’s health status.
- Record AEs and concomitant medication use.
- Review subject’s diaries.
- Assess body weight and vital signs (temperature, pulse rate, respiratory rate, systolic and diastolic blood pressure).
- Collect samples for urine drug screen and urine cotinine tests.
- Perform urine pregnancy test; subjects with positive results must be discontinued from study.
- Perform alcohol breath test.

- The subjects will undergo a supervised overnight fast of at least 10 hours in duration. A light snack will be served on the evening of admission to the clinical facility. No liquid or food intake is allowed during the fast, except water, which is permitted up until 1 hour prior to study drug administration.
- Oral dosing will be done in the clinic for the evening dose in Treatment group “B”.

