## 10.2 Safety Evaluations

AEs and concomitant therapies will be reported during the scheduled office visits. At each treatment office visit, the body weight and vital signs (temperature, pulse rate, respiratory rate, systolic and diastolic blood pressure) will be assessed.

Complete physical and gynecological examinations and routine laboratory evaluations will be repeated at the end of dosing period (Postdosing Day 1) and at the Final Visit and also in case of early discontinuation.

Safety evaluations will be based on the discontinuations due to TEAEs, treatment-induced changes in physical and gynecological examinations, in clinical laboratory test results, in body weight and vital signs, as well as by the incidence and severity of TEAEs reported. TEAEs will be evaluated for the entire study and separately for the two study subperiods (a 28-day dosing cycle and a 28-day postdosing evaluation period).

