## 1. Introduction

This statistical analysis plan (SAP) is intended to give a detailed description of the summaries and the analyses that will be generated for the present study by inVentiv. Analyses specified in this plan are based on (and/or consistent with) Enteris BioPharma study protocol No. LOPDT-ENDO-01 Amendment 03 dated February 01, 2018 (inVentiv Project No. 160218). Safety, tolerability, pharmacokinetic (PK), and pharmacodynamics (PD) analyses will all be described.

The plan may be revised due to unforeseen circumstances and any changes or modifications made after the plan has been finalized will be documented. If additional or revised analyses are required to supplement the planned analyses described in the SAP, the changes and justification for the changes will be outlined in the clinical study report (CSR). No changes will be made without prior approval of the study sponsor. No formal justifications are required for changes to the SAP which do not affect the statistical analysis methods, definitions, or rules defined in this document.

When applicable, all analyses and related processes will be conducted according to inVentiv's Standard Operating Procedures (SOPs). Protocol deviations occurring during the study will be listed.

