## 5. Primary and Secondary Parameters

### Primary Parameters

- Comparative evaluation of safety and tolerability variables, by treatments (refer to Section 9).
- PK parameters as  $C_{max}$ ,  $T_{max}$ ,  $AUC_{0-24}$ ,  $AUC_{0-t}$ ,  $AUC_{0-inf}$ ,  $C_{ss\_oral}$ ,  $C_{ss\_im}$ ,  $K_{el}$ ,  $K_{el\ Lower}$ ,  $K_{el\ Upper}$ , and  $T_{1/2el}$  for leuprolide (refer to Section 10).
- PD parameters derived from LH, FSH,  $E_2$ , and Progesterone levels (refer to Section 11).

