### **9.2 Adverse Events**

Treatment-emergent AEs (TEAEs) and non-TEAEs (those occurring prior to administration of study medication or those first occurred prior to study drug administration and did not worsen in frequency or severity) will be listed. TEAEs will be defined as AEs that occur on or after the date and time of study drug administration, or those that first occur pre-dose but worsen in frequency or severity after study drug administration. TEAEs will be captured through the end of the entire study including two study sub-periods (a 28-day dosing cycle and a 28-day post-dosing evaluation period) or which occur within 30 days following the final examination. In addition, TEAEs with a start date and time during a particular study sub-period will be attributed to the corresponding subperiod.

Serious adverse events (SAEs), which occur during this study or within 30 days following the final examination, will also be listed separately and described in the study report.

The incidence of TEAEs will be summarized for entire study and separately for the two study sub-periods (a 28-day dosing cycle and a 28-day post-dosing evaluation period) using the safety populations for any particular study subperiods. The MedDRA® dictionary Version 20.1 will be used to classify all TEAEs reported during the study by SOC and PT.

Incidence of subjects who experienced TEAEs will be presented by treatment group, by SOC, PT, by investigator-assessed causality (relationship to study drug) and severity. Each subject may only contribute once to each of the incidence rates, for a TEAE following a given treatment, regardless of the number of occurrences; the highest severity or highest causality will be presented, as appropriate. In each summary table, SOC will be presented in descending order of overall incidence rate in terms of frequency of subjects and then in frequency of events (alphabetical order will be used in case of equal rates). For each SOC, PT will be presented the same way. Incidence of TEAEs (number of events) will also be presented by treatment, SOC, and PT, by investigator-assessed causality and severity.

The causality of TEAEs will be classified according to the study protocol as Unrelated, Possibly Related, Probably Related, or Definitely Related. The severity of TEAEs will be rated as per the protocol as mild, moderate, or severe.

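### Treatment D was added without the confinement that A, B and C had, yet SAP 9.2 puts all arms in the same TEAE and ADR tables for the dosing period and whole study without noting the difference

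*SAP*

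**What the plan says.** **Start of dosing.** Under Protocol 7.2, women in A, B and C check in on Day -1 and "will remain domiciled until the completion of all study procedures on Treatment Day 2". For D the Day 1 instruction is "Release subject from the clinical site 2 hours after dosing".

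**End of dosing.** A and B check in on Day 27 at least 11 h before the next morning's dose and "will remain domiciled until the completion of all study procedures on Postdosing Day 1". C and D are not confined then. They attend only on the morning of Postdosing Day 1, which the protocol treats as Treatment Day 29.

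**How AEs are collected.** Protocol 10.2: "AEs and concomitant therapies will be reported during the scheduled office visits". The AE row of Appendix B, read with its treatment-group row, gives Day 2 to A, B and C only, and Days 27 and 28 to A and B only.

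**How AEs are tabulated.** SAP 9.2: "Incidence of subjects who experienced TEAEs will be presented by treatment group". The ADR tables follow the same plan, and both are produced for the whole study and for each subperiod. SAP 5 lists as a primary parameter "Comparative evaluation of safety and tolerability variables, by treatments". SAP 9.4 notes that D has no vital signs on Days -1, 2, 27 and 28. SAP 9.2 has no matching note for AEs.

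**The concern.** A short-lived event in a woman who is on site is seen by staff or reported the same day. The same event at home is recorded only if she remembers it at the next visit or chose to write it in her diary. In D that next visit is Day 8, so anything after the first 2 h of dosing depends on recall or the diary. In A, B and C the first 24 h were spent on site, and in A and B so was the end of dosing.

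Comparative safety is part of the first primary objective, and Protocol 12.5 expects the tolerability data to support dosing selection. D uses a tablet 2.5 times the strength of B's (10 mg against 4 mg, both bid). The likely direction of the distortion is towards the highest dose looking better tolerated than it is. A reader of the tables would have no signal that the arms were observed differently.

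**Working it through.** **1. Does D have a Day 2 contact?** The Day 2 procedures in Protocol 7.2 are headed for A, B and C, but two of their bullets also name D. The protocol's own PK sample counts test this:

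- A and B: 24 × 2 + 3 + 4 = 55, as stated.
- C: 8 + 3 + 1 + 4 = 16, as stated.
- D: 1 + 3 + 1 + 4 = 9.
- Reduction for D: 55 − 9 = 46 samples, and 46 × 3 mL = 138 mL, both as stated.
- With five Day 2 samples D would have 14, and the reduction would be 55 − 14 = 41.

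The stated 46 fits only without Day 2 draws. Appendix B and SAP 9.4 agree with that reading, so it is used below.

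**2. Contacts and scheduled on-site time.** The dosing cycle is 28 × 24 = 672 h. Weekly visits are common to all arms and are left out of the hours.

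| | A and B | C | D |
|---|---|---|---|
| AE reviews to Day 29 | 8 (Days 1, 2, 8, 15, 22, 27, 28, 29) | 6 (Days 1, 2, 8, 15, 22, 29) | 5 (Days 1, 8, 15, 22, 29) |
| Postdosing AE reviews (Days 7, 14, 21, 28) | 4 | 4 | 4 |
| On-site hours after first dose | 24 + 11 + 24 = 59 (8.8%) | 24 (3.6%) | 2 (0.3%) |

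D has 5/8 = 62.5% of the dosing-period reviews of A and B, and 5/6 = 83% of those of C. Over the whole study the shares are 9/12 = 75% and 9/10 = 90%. Against C the gap is one review (Day 2) and 24 − 2 = 22 h. The 59 h is a minimum, because the Day 27 check-in is at least 11 h before dosing.

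**3. Possible size.** The documents give no recall rate, so this step rests on assumptions. Let P be the true TEAE incidence, equal in all arms; f the share of onset risk in the first 24 h; and s the detection of off-site events relative to on-site events.

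- Observed incidence = 1 − exp(−Λd), with Λ = −ln(1 − P) and d = f·d₁ + (1 − f)·r.
- d₁ = 1 in A, B and C; (2 + 22s)/24 in D.
- r = s in C and D; (35 + 613s)/648 in A and B, where 648 = 672 − 24, 35 = 11 + 24 and 613 = 648 − 35.

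Example with P = f = s = 0.5, so Λ = 0.693:

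- D: d = 0.5 × 13/24 + 0.5 × 0.5 = 0.521, observed 30.3%.
- A and B: d = 0.5 + 0.5 × 341.5/648 = 0.764, observed 41.1%.
- C: d = 0.75, observed 40.5%.

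Points by which D falls below A and B:

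| P | f | s = 0.5 | s = 0.7 | s = 0.9 |
|---|---|---|---|---|
| 30% | 3.6% (uniform) | 1.3 | 0.7 | 0.2 |
| 30% | 25% | 3.9 | 2.2 | 0.7 |
| 30% | 50% | 6.9 | 3.9 | 1.2 |
| 50% | 3.6% (uniform) | 2.0 | 1.1 | 0.3 |
| 50% | 25% | 6.3 | 3.3 | 1.0 |
| 50% | 50% | 10.8 | 5.9 | 1.8 |

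Against C the range is 0.1 to 10.2 points, and at most 0.8 if onset is uniform. Every gap above 5 points needs at least a quarter of the onset risk in the first 24 h and s of 0.7 or less.

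**The case against.** **The review count flatters the gap.** Days 1 and 2 are one stay in A, B and C, and Days 27 to 29 are one stay in A and B. Counted as episodes, every arm has five: start, Days 8, 15, 22 and end. The recall intervals are 6, 7, 7 and 5 days in A and B, 6, 7, 7 and 7 in C, and 7, 7, 7 and 7 in D. This stands. The real difference is the first 24 h and, against A and B only, the last 35 h or so.

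**The diary helps.** Diaries are reviewed at Days 8, 15 and 22 in all arms and can hold clinically notable events. This is partial mitigation: such entries are optional, and the only hand-out step listed is in the Day 2 procedures headed for A, B and C.

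**The tables are descriptive and the groups small.** No inferential analysis is planned, and the groups are 9, 9, 5 and up to 12. For illustrative counts, exact 95% intervals are 21-79% for 6/12, 14-79% for 4/9 and 5-85% for 2/5. The largest modelled gap, 10.8 points, is about 1.3 women in 12. Imprecision does limit what the tables can show, but it does not remove a systematic difference in observation, and readers will compare the percentages directly.

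**Stronger readings the documents do not support.** A reader might infer that visits were taken away from D. They were not: "This protocol amendment include a fourth arm, which will be a 10 mg Leuprolide Oral Tablet administered BID for 28 days", and that arm never had them. That this is the amendment the SAP cites, "Amendment 03 dated February 01, 2018", is likely but not said in words. A reader might also take the vomiting withdrawal as an early event of the kind D would miss. Its arm is not stated, and its timing, given as post-dose Day 1, could mean Day 1 or Day 29.

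**Conclusion.** The point holds as a reporting gap. D is observed less than every other arm during dosing, SAP 9.2 tabulates it beside them without comment, and the comparison is a primary parameter. The full gap is against A and B. Against C it is Day 2 and about 22 h on site. Only the dosing-period and whole-study tables are affected, since postdosing reviews are equal.

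The AE window itself is the same in all arms, so the loss is under-recall and not missing follow-up. Its size is unknown. Under the assumptions above it is 0.2 to 10.8 points against A and B for any TEAE, and at most about 2 points if onset is uniform. A reader might infer that a large spurious benefit for D has been shown. It has not: the upper end needs both clustering on the first day and poor recall, and the documents support neither figure. D is also non-randomised, so matching the questioning removes this one difference and no other.

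**What to change.** In SAP 9.2:

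1. Keep the full-period TEAE and ADR tables. Footnote the dosing-period and whole-study versions with the number of AE contacts and the scheduled on-site hours by arm.
2. Add one supportive TEAE table and one supportive ADR table limited to onset on Treatment Days 3-21. In every arm those days are asked about at the same outpatient visits, on Days 8, 15 and 22. Read D against A, B and C on these alongside the full-period tables.
3. Show events with onset on Days 1-2 and on Days 22-29 as separate rows, labelled by arm as domiciled or outpatient.

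Define the window by onset date. Protocol 11.2 lists only the date of onset among the AE items to collect, so cuts by clock time may not be possible even though SAP 9.2 refers to start times.

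In the protocol, reconcile the Day 2 procedures that name D with Appendix B and SAP 9.4, and state when D receives the diary. If D does have a Day 2 contact, its review count becomes 6 and the footnote changes.

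The cost is SAP wording and two extra tables, with no new data. The downside is that the matched tables cover 19 of 28 dosing days (68%) and leave first-day events to the labelled rows, where the arms still differ in observation.

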### 9.3 Laboratory Parameters

Clinical laboratory (hematology and serum chemistry) results will be obtained at screening, end of dosing period (Post-dosing Day 1) and at the Final Visit and also in case of early discontinuation. Urinalysis results will be obtained only at screening and final visit (or early discontinuation).

Listings of all clinical laboratory results will be provided with the abnormal values flagged with "L" for low and "H" for high for continuous parameters, and "A" for abnormal for categorical parameters.

Descriptive statistics (mean, median, SD, Min, Max, and sample size "n") for each clinical laboratory test (continuous variables) will be presented for screening and final visit, and by treatment for Post-dosing Day 1 timepoint. Change from screening will also be presented. For categorical variable (urinalysis test), the number of subjects (frequency and percentage) will be tabulated by results (e.g. negative, positive, trace). A summary table of shifts from screening to final visit will be provided. The shift tables will include normal, low, and high values relative to the laboratory reference ranges (or normal-abnormal for categorical variables). Results from repeat tests will not be included in the summary statistics unless the repeat was required (and documented as such) due to technical reasons or an invalid initial result.

Note: all analyses described above will be performed by treatment group for the entire study and separately for the two study subperiods (a 28-day dosing cycle and a 28-day postdosing evaluation period).

In the analyses for the entire study duration, laboratory results from pre-study screening and final study visits will be used. In the analyses for the 28-day dosing cycle, laboratory results from pre-study screening and end-of-dosing study visits will be used. In the analyses for the 28-day postdosing evaluation period, laboratory results from end-of-dosing and final study visits will be used.

### 9.4 Vital Signs and Body Weight

Vital signs measurements (temperature, heart rate, respiratory rate, systolic and diastolic blood pressure) and body weight will be performed at screening, Days -1, 1, 2, 8, 15, 22, 27, 28 ; PD Days 1, 7, 14, 21 and 28 (Final Visit) or Early Discontinuation Visit. Note: No evaluations on Days -1, 2, 27, and 28 will be performed for Treatment "D".

A listing of all vital signs and body weight results will be provided.

Descriptive statistics (mean, median, SD, Min, Max, and sample size) will be presented for screening and final visit (or early discontinuation visit), and by the associated current treatment for other evaluation timepoints, for each vital sign measurement and body weight.

Note: all analyses described above will be performed by treatment group for the entire study and separately for the two study subperiods (a 28-day dosing cycle and a 28-day postdosing evaluation period).

In the analyses for the entire study duration, vital sign and body weight results from pre-study screening and final study visits will be used. In the analyses for the 28-day dosing cycle, vital sign and body weight results from pre-study screening through end-of-dosing study visits will be used. In the analyses for the 28-day postdosing evaluation period, vital sign and body weight results from end-of-dosing through final study visits will be used.

Change from baseline (or change from screening for the final visit) will also be presented. Baseline will be defined as the last results (scheduled or unscheduled) obtained prior to first study drug administration. Results from post-dose repeat tests will not be included in the summary statistics unless the repeat was required (and documented as such) due to technical reasons or an invalid initial result.

### **9.5 Electrocardiogram**

Twelve-lead ECGs will be performed at screening and final visit (or early discontinuation).

A listing of all ECG results will be provided.

Descriptive statistics (mean, median, SD, Min, Max, and sample size “n”) will be presented for each timepoint for each ECG measurement as per data availability. Also, change from screening descriptive statistics for final visit will be presented. Results from repeat tests will not be included in the summary statistics unless the repeat was required (and documented as such) due to technical reasons or an invalid initial result.

## **10. Pharmacokinetic Analyses**

Shells for all summary descriptive statistic tables and listings referred to in this section are displayed in the document containing the TFL shells; the shells may be revised as they are presented to illustrate the general layout of data to be included in the final report.

The primary statistical analyses of PK data will be conducted on the primary PK population. Supportive statistical analyses of PK data will be conducted on the supportive PK population.

